^b Randomized patients who meet 1 or more of the study discontinuation or withdrawal criteria (Section 5.4) should be invited to perform the ET visit as soon as possible. An EOT visit will be conducted at 4 weeks after the last dose of IMP (±1 week), and a FU visit for safety evaluation will be conducted at 8 weeks (-1/+2 weeks) after the last dose of IMP. Since TV-44749 is an LAI, additional antipsychotic treatment is not required for 4 weeks following the last dosing visit (unless clinically indicated), whereas during the subsequent 4 weeks (FU period), patients may be treated for schizophrenia according to the investigator's judgment.

^c Other procedures may be performed according to the discretion of the investigator. However, in order to reduce patient burden and to avoid unnecessary data collection, the investigator will have discretion in determining whether all unscheduled visit procedures should be performed during the unscheduled visit in the event that (i) the unscheduled visit is one of multiple in-clinic visits that are deemed necessary in close proximity (ie, 2 or more visits within 1 week) or (ii) the visit is for administrative purposes (eg, reconsenting) or technical reasons (eg, repeat laboratory sample collection for reasons unrelated to an adverse event) and not due to a change in the patient's medical status per clinical judgment.

^d All patients will be hospitalized upon study entry (screening) and will remain hospitalized during the screening period and for the first 4 weeks after randomization (until the second IMP administration). After the second injection, patients may be discharged if all discharge criteria are met and if, in the opinion of the investigator, discharge is appropriate. During the hospitalization period (ie, before the patient is discharged), a short-term leave from the site may

Clinical Study Protocol with Amendment 01

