4. STUDY DESIGN

4.1. General Study Design and Study Schematic Diagram

This is a Phase 3, multinational, multicenter, randomized, double-blind, parallel-group, placebo-controlled study with an open-label, long-term safety phase to evaluate the efficacy, safety, and tolerability of olanzapine for extended-release injectable suspension (TV-44749) for sc use as treatment of adult patients with schizophrenia.

The study will be composed of 2 periods ([Figure 1](#)): Period 1 (the double-blind, placebo-controlled, efficacy and safety period [acute treatment phase]) and Period 2 (open-label safety period [long-term safety phase]). For each patient, the duration of Period 1 will be 8 weeks, and the duration of Period 2 will be up to 48 weeks.

Patients will be randomized to the 8-week efficacy and safety period (acute treatment phase; Period 1) to 1 of 3 active treatment groups (low [318 mg q1m], medium [425 mg q1m], or high dose [531 mg q1m]) or the placebo group in a 1:1:1:1 ratio.

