procedures are performed. Patients will be asked to consent to share their information with a vendor that will verify that they are not currently participating or have not recently participated in another clinical study, unless prohibited by local requirements. [REDACTED]

[REDACTED]

[REDACTED]

[REDACTED]

[REDACTED]

Patients with exacerbation that started \leq 8 weeks prior to screening (the investigator should confirm the exacerbation based on the patient's medical records and/or based on anamnesis) and who would benefit from psychiatric hospitalization or continued hospitalization for symptoms of schizophrenia may be included in this study.

The patient's total Positive and Negative Syndrome Scale (PANSS) score should be between 80 and 120, inclusive, at screening with a score \geq 4 on at least 2 of the following 4 items of the PANSS positive subscale: hallucinatory behavior, delusions, conceptual disorganization, or suspiciousness/persecution.

Patients must have an identified responsible person (referred to as the caregiver) who has agreed to provide information about the patient's location, condition, and overall status during outpatient portions of the study during Period 1. The site personnel must identify the caregiver at the screening visit and consider the caregiver a reliable contact person. The caregiver must have regular contact with the patient (defined as direct contact not fewer than 3 times per week), with the expectation that this frequency of contact would continue throughout the outpatient portion of Period 1 (it is also advised during the rest of the study, including Period 2 and the FU period). The patient's caregiver will be asked to sign a caregiver ICF during the screening period.

Patients who are not already in an inpatient setting will be hospitalized during the screening period (see details pertaining to hospitalization duration and discharge criteria in the description of "Period 1" below).

Patients will taper off their prior oral antipsychotic medications at rates per the investigator's discretion. The tapering-off process should be completed prior to randomization.

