Detailed procedures regarding dose adjustments will be provided in the pharmacy manual and in any other study plans as applicable.

Section [6.9.4](#) provides details for dose adjustment following outcome of primary endpoint analysis.

Procedures for Potential Post-injection Delirium/Sedation Syndrome

Early Termination and Follow-up Period

Randomized patients who meet 1 or more of the study discontinuation or withdrawal criteria (Section 5.4) should be invited to perform the ET visit as soon as possible. An EOT visit will be conducted at 4 weeks after the last dose of IMP, and a FU visit for safety evaluation will be conducted at 8 weeks after the last dose of IMP. The time window for the EOT visit is ± 1 week, and the time window for the FU visit is $-1/+2$ weeks. Since TV-44749 is an LAI, additional antipsychotic treatment is not required for 4 weeks following the last dosing visit (unless clinically indicated), whereas during the subsequent 4 weeks (FU period), patients may be treated for schizophrenia according to the investigator's judgment. In case the ET visit is conducted during the time window of the EOT visit, the ET and EOT visits may be conducted on the same day (ie, the visits will be combined, and all assessments listed in the Study Procedures and Assessments tables [Table 1 or Table 2] for the ET and EOT visits must be performed). Patients who discontinue study treatment should be encouraged to complete the remaining visits until completion of the study (ie, ET, EOT, and FU visits).

In case the sponsor decides to stop the study, active randomized patients will be asked to complete the EOT visit 4 weeks after the last dose of IMP and a FU visit 8 weeks after the last dose of IMP. The time window for the EOT visit is ± 1 week, and the time window for the FU visit is $-1/+2$ weeks.

The total duration of patient participation in the study will include up to 8 days of screening, during which oral olanzapine will be administered for 2 consecutive days (to establish tolerability), 8 weeks of treatment with TV-44749 or placebo (Period 1 [acute treatment phase]), up to 48 weeks of treatment with TV-44749 (Period 2 [long-term safety phase]), and 4 weeks of FU.

The end of study is defined as the last visit of the last patient.

The study duration will be from Q4 2022 (first patient screened) to Q2 2025 (last patient last visit).

The study schematic diagram is presented in [Figure 1](#).

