5.2. Patient Exclusion Criteria

Patients will not be randomized in this study if they meet any of the following criteria:

- a. The patient has a current clinically significant DSM-5 diagnosis other than schizophrenia (has a primary current diagnosis other than schizophrenia or a comorbid diagnosis that is primarily responsible for the current symptoms and functional impairment).
- b. The patient has a known history of the following: (a) borderline personality disorder, antisocial personality disorder, or bipolar disorder; (b) traumatic brain injury causing ongoing cognitive difficulties, Alzheimer’s disease, or another form of dementia, or any chronic organic disease of the central nervous system; and (c) intellectual disability of a severity that would impact ability to participate in the study.
- c. The patient has an improvement (reduction) in the total PANSS score of $\geq 20\%$ between screening and day 1 (baseline [randomization] visit).
- d. The patient was hospitalized for >14 days (with the exception of social or administrative hospitalization) in the current exacerbation episode prior to screening.
- e. The patient has a significant risk of violent behavior based on the patient’s medical history or investigator’s judgment.
- f. The patient has a significant risk of committing suicide based on the patient’s medical history or C-SSRS, and the investigator’s judgment.

Patients with a C-SSRS positive response to suicidal ideation items 3, 4, or 5 and/or positive suicidal behavior response in the past 6 months are not eligible.

- g. The patient meets criteria for moderate to severe substance use disorder (based on DSM-5 criteria) within the past 6 months, such as chronic alcohol abuse or drug abuse (excluding those related to caffeine or nicotine). If, per the investigator’s judgment, a patient does not meet the criteria for substance use disorder, a positive result on the urine drug test is not exclusionary. Patients’ eligibility in such case of positive result, without medical explanation, will be determined by the investigator based on the patient’s background, history of substance use, and the investigator’s

discussions with family members, caregivers, or healthcare professionals, as applicable.

- h. The patient is currently using an LAI antipsychotic or is still under the coverage period of the specific LAI at time of screening.

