5.4. Withdrawal Criteria and Assessments/Procedures for the Patient

Patients are expected to participate in the study for its entire duration and perform the scheduled visits and procedures. Each patient is free to withdraw from the study or discontinue treatment with IMP at any time, without prejudice to their continued care, but every effort should be undertaken to determine the reason for discontinuation.

Patients must discontinue treatment with IMP and/or withdraw from the study if any of the following events occur:

1. Patient withdraws consent or requests discontinuation from the IMP and/or withdrawal from the study for any reason.
2. Patient develops an illness that would interfere with his/her continued participation.
3. Patient is noncompliant with the study procedures and assessments or administration of IMPs in the opinion of the investigator.
4. Patient takes prohibited concomitant medications as defined in this protocol (final decision to withdraw the patient will be on a case-by-case basis per sponsor discretion).
5. A female patient has a confirmation of pregnancy during the study from a positive pregnancy test.
6. The sponsor requests withdrawal of the patient.
7. Patient experiences an adverse event or other medical condition which indicates to the investigator that continued participation is not in the best interest of the patient.

Additionally, patients who meet the following study-specific criteria will be early terminated (ie, discontinued from further treatment with IMP and encouraged to complete the EOT and FU visits):

1. Patient is diagnosed with a clinically significant DSM-5 disorder other than schizophrenia.
2. A patient demonstrates a significant clinical deterioration that cannot be managed with permitted rescue medication as judged by the investigator based on any relevant history or observation made by the investigative site, and/ or requires other antipsychotic treatment apart from TV-44749. Hospitalization due to deterioration of schizophrenia that does not require other antipsychotic treatment will not be a withdrawal criterion unless determined as such by the investigator.
3. A patient experiences 3 events of pus-containing lesions (abscess, infection, or inflammation) at the site of injection requiring intervention/systemic treatment following 3 separate IMP injections.

Patients should be treated with standard of care after withdrawal from or termination of the study as appropriate.

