6.3.2. Justification for Use of Placebo Investigational Medicinal Product

Based on the pre-Investigational New Drug meeting with the Food and Drug Administration (FDA) in 2019, the Agency recommended that the sponsor conduct a prospective, randomized, placebo-controlled study to assess the safety and efficacy of TV-44749, with a primary endpoint of symptom severity, as measured by PANSS, at 8 weeks.

The use of a placebo control treatment group for comparison is acceptable and commonly used in clinical studies assessing efficacy in patients with schizophrenia ([Nasser et al 2016](#), [Potkin et al 2020](#)).

Several measures to ensure adequate treatment of patients assigned to the placebo group are included in the study protocol. Patients will be treated with placebo for a limited period (8 weeks). All patients will be hospitalized and closely monitored for at least 4 weeks following the first IMP administration ([Table 1](#)). Patients who fail to meet discharge criteria (RDQ) at this point may continue as inpatients until the end of Period 1 (week 8), at which point active treatment will be administered to all patients who meet Period 2 entry criteria. Throughout Period 1 (placebo-controlled period), rescue medications use will be allowed per investigator clinical judgment ([Section 6.7.1.1](#)). At all times, patients may be withdrawn from the study per investigator discretion if participation in the study no longer provides a potential clinical benefit to the patient or per patient's request for any reason ([Section 5.4](#)). If a patient is withdrawn from the study at investigator discretion, patients will be advised to return to their primary physician for treatment continuation consideration.

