In cases when knowledge of the IMP assignment is needed to make treatment decisions during Period 1, the investigator may unblind the patient's IMP assignment as deemed necessary, mainly in emergency situations. Individual randomization codes indicating the IMP assignment for each randomized patient will be available to the investigator(s) or pharmacist(s) at the investigational center via the RTSM, via internet. A back-up process will be available to the investigator in case of internet connection issues. Breaking of the treatment code can always be performed by the investigator without prior approval by the sponsor; however, the sponsor should be notified following the breaking of the treatment code during Period 1. The patient's IMP assignment should not be revealed to the sponsor (during Period 1).

If a blind is broken during Period 1, the patient will be withdrawn from the study, and the event will be recorded on the CRF. The circumstances leading to the breaking of the code should be fully documented in the investigator's study files and in the patient's source documentation. Assignment of IMP during Period 1 should not be recorded in any study documents or source document.

In blinded studies, for an adverse event defined as a suspected unexpected serious adverse reaction (SUSAR) (ie, reasonable possibility; see Section 8.1.4), the Global Patient Safety and Pharmacovigilance (GPSP) may independently request that the blind code be broken (on a case-by-case basis) to comply with regulatory requirements. The report will be provided in an unblinded manner for regulatory submission. If this occurs during Period 1, blinding will be maintained for the investigator and for other personnel involved in the conduct of the study and in the analysis and reporting of the data.

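### In blinded Period 1, the depot-cover reason for not requiring another antipsychotic after a patient stops is wrong for the one in four on placebo

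*Protocol*

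**What the plan says.** Footnote b of Table 1 (Protocol 1.3, the Period 1 schedule) addresses randomized patients who meet a discontinuation or withdrawal criterion and gives one rule for all of them: "Since TV-44749 is an LAI, additional antipsychotic treatment is not required for 4 weeks following the last dosing visit (unless clinically indicated"). It contrasts this with the next four weeks, the follow-up period, when the investigator may treat as he or she judges best. The early-termination subsection of Protocol 4.1, which serves both periods, has the same rule: "additional antipsychotic treatment is not required for 4 weeks following the last dosing visit (unless clinically indicated"). SAP 2.1 repeats it. None of the three places separates active from placebo, or Period 1 from Period 2. Table 2 footnote b carries the sentence for Period 2.

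On who has depot cover in Period 1:

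- Patients are allocated to three TV-44749 doses "or the placebo group in a 1:1:1:1 ratio" (Protocol 4.1).
- The placebo vial contains no olanzapine powder (Protocol 6.2.1).
- On earlier oral antipsychotics: "The tapering-off process should be completed prior to randomization" (Protocol 4.1, screening).
- Exclusion criterion h (Protocol 5.2) reads: "The patient is currently using an LAI antipsychotic or is still under the coverage period of the specific LAI at time of screening".
- Investigators are blinded (Protocol 6.9).

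On care after a stop:

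- Protocol 5.4: "Patients should be treated with standard of care after withdrawal from or termination of the study as appropriate".
- Protocol 6.3.2: "Several measures to ensure adequate treatment of patients assigned to the placebo group are included in the study protocol".
- Protocol 6.10.2 lets the investigator break the code when "knowledge of the IMP assignment is needed to make treatment decisions during Period 1".

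**The concern.** The rule rests on a single reason: the drug given is long-acting, so the patient remains covered for a month after the last injection. A placebo patient was given no drug. Because Period 1 is blinded, the investigator cannot tell which stopping patients the reason fits.

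What is at stake is clinical. Patients enter with an acute exacerbation, a PANSS total of 80 to 120 and a CGI-S of at least 4 (Protocol 5.1). An investigator who takes the reason at face value would assume cover that one in four do not have, and might wait for the follow-up period before resuming routine treatment.

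**Working it through.** **1. Does any other source of cover make the reason true for placebo?** No. The vial is empty, earlier oral antipsychotics are to be tapered off before randomization, and patients still covered by another LAI are excluded. Some patients take two oral olanzapine doses during screening, the second at least 24 hours before randomization. With a mean oral half-life of 30 hours (Protocol 2.2.2.1.4.1), these give no month-long cover.

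**2. Same sentence, two periods.**

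| Place | Who has received TV-44749 | Reason given |
|---|---|---|
| Table 1 footnote b (Period 1) | three of four arms | wrong for the fourth |
| Table 2 footnote b (Period 2) | everyone | right |
| Protocol 4.1 and SAP 2.1 (both periods) | depends on the period | right only for Period 2 |

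**3. Length of the window.** The 4 weeks run from the last dosing visit, not from the stop. Injections are nominally on Days 1 and 29, so the windows end on Day 1 + 28 = Day 29 and Day 29 + 28 = Day 57. A patient stopping on Day 22 has 29 − 22 = 7 days left. Over all stopping times, 0 to about 4 weeks remain.

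**4. Number of patients.**

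- Placebo share: 1/(1+1+1+1) = 25%. Of 640 planned (Protocol 10.1): 640/4 = 160 placebo and 480 active. Of the 675 randomized by 29 January 2024 (Protocol Amendment Details): 675/4 = 168.75, about 169. The option of later active-only enrolment was not used (SAP 6.1), so the share is not diluted.
- The planned early-termination rate is redacted. From 440 completers of 640 it is (640 − 440)/640 = 31.25%.
- If equal across arms (assumption): 160 × 0.3125 = 50 placebo and 480 × 0.3125 = 150 active patients stop.
- Some placebo stops already fall under the clinical-indication exception. If that is 25% to 75% of them (assumption), 50 × 0.25 = 12.5 to 50 × 0.75 = 37.5 remain, about 13 to 38.
- If the placebo stopping rate is 20% to 45% (assumption), 160 × 0.20 = 32 to 160 × 0.45 = 72 stop. With the same exception shares, 32 × 0.25 = 8 to 72 × 0.75 = 54 remain.

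These count patients for whom the reason is wrong. They do not count patients left untreated.

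**5. Effect on the analysis.** Under SAP 1.2.1, data after treatment discontinuation are removed and imputed, and antipsychotic use after early termination is not an intercurrent event. The primary estimand is therefore unaffected.

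**6. Who was still in Period 1.** Amendment 01 is dated 15 February 2024. Going back 56 days gives 21 December 2023, so only patients randomized after about that date were still within 8 weeks. Those randomized by 29 January 2024 reach week 8 by about 25 March 2024.

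**The case against.** The case for leaving the text alone is substantial. Footnote b itself points to Section 5.4, which calls for standard of care after withdrawal in every arm. Section 5.4 also terminates patients whose deterioration cannot be managed with rescue medication or who need another antipsychotic, and both are indications to treat. Section 6.3.2 adds referral to the primary physician when the investigator withdraws a patient. The code can be broken without sponsor approval, and a patient who is already stopping loses nothing by it. Blinded investigators know the allocation ratio. Three in four stoppers do carry a depot, and a default of not requiring more drug protects them from overlapping exposure.

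All of this stands as a limit on the harm. None of it makes the reason true. Section 5.4 says as appropriate, and the footnote informs what looks appropriate. Section 6.10.2 describes code-breaking as mainly for emergencies, and a reader who trusts the footnote has no prompt to use it. The list in 6.3.2 nowhere warns that cover may be absent after a stop.

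A reader might infer that the Protocol bars treatment of placebo patients for a month, or that its sections contradict each other. The documents support neither. The wording is that treatment is not required, clinical indication is not confined to deterioration and can include possible lack of cover, and 5.4 is compatible with the sentence.

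**Conclusion.** The point holds as a wrong premise for one arm of blinded Period 1. It is worth correcting because the population is acutely ill and the correction is cheap. It is a point to consider, not a flaw in the trial's inference.

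The 25% share follows directly from the allocation ratio. The figure of about 50 placebo stops rests on a back-calculated overall rate and on equal stopping across arms, and is at the upper end because it includes patients already under the exception. It is tempting to read it as about 50 patients left without treatment. The documents do not support that: no section shows that any investigator relied on the sentence, and the number untreated cannot be estimated. It would also be wrong to read the rule as four weeks without treatment from the date of stopping, or to infer any bias in the primary result.

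**What to change.** - **Table 1 footnote b:** replace the LAI reason. State that the patient may have received TV-44749 or placebo, so depot cover can be neither assumed nor excluded. Leave antipsychotic treatment to the investigator's judgment, preferably after the early-termination assessments but at any time if clinically indicated.
- **Protocol 4.1, early-termination subsection:** split the sentence by period, because simple replacement would remove a reason that is valid in Period 2. Use the new wording for Period 1.
- **SAP 2.1:** match it, so that the documents agree.
- **Table 2 footnote b:** leave unchanged.

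The wording discloses no allocation. The cost is a few sentences, for example by administrative letter; Administrative Letter 03 already changed footnote b in this way. The primary analysis does not change. Few patients were still in Period 1 at Amendment 01, so the practical gain within this trial was small by then.

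There are two downsides. First, earlier treatment may overlap with an olanzapine depot in active-arm stoppers (about 150 under the equal-rate assumption), which is why the text must not exclude cover. Second, for a stop after the second injection, the end-of-treatment visit falls at about Day 57, which is week 8. SAP 4.4 maps an in-window result to a missing week 8 visit, and the supplementary treatment policy analysis (SAP 1.2.3) uses data regardless of intercurrent events. Earlier antipsychotic use could therefore influence some week 8 scores in that analysis.
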